#### Procedures for Phase II: The Randomized Clinical Trial

One hundred adolescents (11-18 years of age) with a self-reported act of selfharm in the past 6 months will be recruited into the study. Following screening, consent and baseline assessment, the adolescents and their families will be randomly assigned to either the (1) Technology assisted -CIFFTA or 2) Treatment As Usual. The comparison condition was selected to test our intervention against a standard of care in the community which is usually delivered in the traditional face-to-face method with no technology. CIFFTA treatment services will be delivered at the Institute for Individual and Family Counseling (IIFC), which is a training clinic for graduate students in the School of Education and Human Development at the University of Miami or virtually via HIPAA compliant Zoom. The IIFC provides affordable counseling services to the local community and serving as a center for counseling research. Families randomized to TAU will be referred to services in the community which will be delivered in person or virtually via HIPAA compliant Zoom. Randomization will be stratified by gender, type of self-harm, trauma exposure and LGBT status. During the treatment phase, the two conditions will be tested as 16 week interventions. We will not try to match face to face intervention hours but we will try to match overall contact hours (in the experimental condition some of these hours will be with technology). During the "continuing care"

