
#### Therapist Supervision and Adherence Monitoring. Weekly clinical

supervision/consultation meetings will be held for the CA-CIFFTA, led by [name]. Recorded therapy sessions will be reviewed and good manual implementation will be emphasized. In the CA-CIFFTA condition, reports generated weekly showing usage (in minutes) of the web-based components will be reviewed. An independent adherence rater trained to rate therapy sessions will randomly select 20% of the CA CIFFTA sessions at different phases (early, mid, and late) of treatment. Ratings that fall below adequacy on any dimension/component will trigger increased supervision focus for that dimension and if necessary, re-training. The condition supervisor will be the gold-standard for inter-rater reliability on adherence ratings and raters will be trained to achieve an intra-class correlation coefficient of .70 or higher, and at least 80% agreement across items. Interrater reliability will be checked regularly to avoid drift.

Prevention of Dropouts from the study. To ensure sample retention procedures include: 1) conducting assessments at convenient locations when necessary(e.g., homes), 2) paying families for their participation in assessments, 3) conducting service utilization phone interviews between the T2 and T3 assessments and updating all contact information at regular intervals, 5) obtaining the names of three contact persons who may be contacted by the Assessment Specialist when the family is unreachable (included in the consent form), and 6) sending out birthday and holiday cards to all participants. In our experience, the utilization of such procedures for tracking and contacting participants dramatically increase retention rates in the study. In our previous large NIDA randomized trial with high–risk Hispanic youth with Substance Abuse Disorder, we were successful at obtaining approximately 75% of the caregiver and 70% of the adolescent scheduled assessments 16 months after baseline.

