Adaptations for youth who report being LGBTQ and/or exposed to trauma, and families. CIFFTA's design lends itself to adaption to diverse populations. Its logic and emphasis on tailoring facilitates the treatment's extension to new populations with unique stressors. During the development phase of this study (first 7 months) we will build on existing modules. Some of the expected adaptations will focus on modules for kids on how they can cope with stressors related to LGBT-related rejection and alienation, emotion regulation and distress tolerance for ameliorating self-harm behaviors, using evidencebased coping strategies for risk factors result from exposure to traumatic events (see Seeking Safety strategies). A module for parents who are having a hard time accepting their son's/daughters being a gender/sexual minority youth will help them to understand the normative stages some parents must go through, allow parents to express their concerns, distress, and fears, so that they are more ready to have a productive family therapy session with their sons and daughters. A parallel module may be offered to youth to increase their readiness to have a family session in which a loving and caring relationship can be created.

Measures: Measures have been selected for: 1) Screening; 2) Ultimate Adolescent Outcomes, e.g., Self-harm; 3) Immediate Outcomes, e.g., depression, emotion regulation, family conflict, and substance use; 4) Cultural Factors; and 5) Additional Measures, e.g., trauma, minority stress. Measures will be administered at Screening, Baseline (T1) 4 months after baseline (Termination or T2), and 12 months after baseline (T3). Spanish versions of the measures are available. Every effort has been made to reduce participant burden. The total battery is expected to take 90 minutes to administer to youth and 40 minutes to parents. These will be administered in person or via HIPAA compliant Zoom. Measures are attached.

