## 25) Local Number of Subjects

A total of 100 youth will be accrued locally. The participants' families will also be included in the study.

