## 30) Consent Process

For those families that meet the inclusion/exclusion criteria and are interested in participating in the research study, the study assessor will obtain a second assent

from the adolescent and informed consent from her/his primary caregiver to participate in the randomized trial. The assessor will provide the adolescent and family members with a copy of the consent and assent forms in person or via Zoom with the screen share option, and, because subjects may have a low level of literacy, will then read the consent and assent forms out loud. Consent and assent forms will also be emailed to the family. The study assessor will explain to the adolescent and her/his family the purpose and procedures of the study. All of their family members will be asked if they are willing to participate in this study. Adolescents and caregivers will be asked if they are willing to be randomly assigned into one of two treatment conditions: CA CIFFTA or TAU. The assessor will explain that they have no way of predicting which family will receive which kind of treatment because this is established by chance (as if by the flip of a coin). If the family decides to participate, they will get paid \$75 at T2 and \$100 at T3. The nature of the confidentiality that surrounds research studies will be discussed with the adolescent and family members, explaining that confidentiality is assured to the extent allowed by law. Specifically, that the information they provide is strictly confidential, except for the case of potential abuse of a child, or danger to their own lives or that of others. The adolescent and family members will be informed that information collected from the research instruments will be used only for research purposes and reported in aggregate form and composite case studies (a strategy for creating case studies in which several cases are integrated into a single case study and all identifiers are removed, to protect confidentiality). They will also be informed that therapy sessions will be videotaped, and they will be asked to provide permission for videotaping sessions for supervision, research, and training. Consent and assent forms clearly specify that any family member has the right to request that their videotapes, and corresponding transcripts be erased/destroyed in part, or in whole at any time during the course of the study or thereafter. In addition, informed consent and assent will be obtained allowing research study staff to call three persons who are close to the adolescent and family members for the purpose of contacting families that may be unreachable at any of the assessment time points.

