NCT03709472

Computer Assisted Family Intervention to Treat Self-Harm Disparities in Latinas and Sexual/Gender Minority Youth

Statistical Analysis Plan 8/21/24

Data were analyzed using SPSS Version 29 (IBM, 2023). We began our analyses by documenting the number of session and hours of treatment to assess CIFFTA's feasibility and acceptability. We conducted logistic regressions to examine whether baseline characteristics predicted those participants who successfully reached termination and T2 assessments. To examine whether changes in adolescent symptoms of depression over time differed by treatment, a mixed ANOVA was used with depression scores as the within-subjects variable and treatment condition as the between-subjects variable. We used the same analytic strategy to determine whether changes in emotion regulation and family connectedness differed over time by treatment. A series of mixed ANOVAs were used with the Total scores from the PHQ-9, the Difficulty with Emotion Regulation Scale and the Family Connectedness Scale as the within-subjects variables and treatment condition as the between-subjects variable. When effect sizes are reported, cutoffs for partial eta-squared effect sizes are small .01, moderate .06, large .14. Additionally, Chi-Square Tests of Association were used to determine whether the proportion of youth endorsing whether they could talk to their parent about problems differed over time. This analysis was conducted by condition examining mothers and fathers separately.

A complementary analytic strategy was used to investigate change in youth who entered the study with presenting problems in the clinical range at baseline assessments based on established clinical cutoffs (i e., those with at least mild levels of depression at baseline). Descriptive statistics were used to determine the rates of suicidal thoughts and self-harm at baseline and termination by condition. In addition, Chi-Square Tests of Association were used to determine whether the proportion of youth endorsing thoughts of suicide differed by treatment condition.

We also used the Reliable Change Index (RCI) to determine whether the magnitude of change was statistically reliable rather than due to random fluctuations caused by measurement error (Jacobson & Traux, 1991). We examined symptoms of depression.

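### Suicidal thoughts are compared between arms by an unadjusted chi-square although the baseline value is on file: a valid test that gives up some precision and leaves any chance baseline gap in the result

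*SAP*

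**What the plan says.** The second paragraph of the SAP deals with suicidal thoughts in two sentences. The first is descriptive: "Descriptive statistics were used to determine the rates of suicidal thoughts and self-harm at baseline and termination by condition". The second gives the comparison: "Chi-Square Tests of Association were used to determine whether the proportion of youth endorsing thoughts of suicide differed by treatment condition". It names no covariate, stratum or time point.

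The same paragraph opens with a subgroup: "A complementary analytic strategy was used to investigate change in youth who entered the study with presenting problems in the clinical range". The text does not say whether the chi-square is confined to that subgroup. By contrast, the last paragraph of the SAP does say that its models use the full sample.

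In the protocol (section 10, Procedures for Phase II), "Randomization will be stratified by gender, type of self-harm, trauma exposure and LGBT status". Baseline suicidal thoughts are not among these factors. The only covariate-adjusted models that the SAP sets out for an outcome, in its last paragraph, have past-month self-harm as the outcome, adjust for gender and LGBTQ status, and list no treatment term. Section 9 of the protocol lists self-harm as primary and five secondary endpoints; suicidal thoughts are not among them.

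**The concern.** A baseline measurement of the same item is often related to the later one, and here it is already in the dataset. For depression, emotion regulation and family connectedness, the SAP brings the baseline value into the comparison through a mixed ANOVA. For suicidal thoughts it does not.

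Two things are at stake. First, part of the outcome variance that baseline could explain stays in the error term, so the comparison has less power than the same data could give. Second, with arms this small a sizeable baseline gap can arise by chance, and a reader of the termination percentages cannot tell how much of a difference was there at the start. A chi-square also supplies only a p-value, with no effect estimate or interval. This is the SAP's only stated between-arm test on a suicide-related outcome, so readers are likely to look at it.

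**Working it through.** The plan has no power or event-rate figure to reproduce: the sample size is given without alpha, power or effect size.

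**Inputs from the documents**
- Sample size (protocol section 25): "A total of 100 youth will be accrued locally".
- Allocation (protocol section 30): "this is established by chance (as if by the flip of a coin". No ratio is given as a number; I assume 1:1, so 50 per arm.
- Retention: no planned dropout rate. The only guide is an earlier trial (section 10, prevention of dropouts), with about "70% of the adolescent scheduled assessments 16 months after baseline". Used as a proxy: 100 × 0.70 = 70, or 35 per arm.
- Termination (section 10, Measures): "4 months after baseline (Termination or T2), and 12 months after baseline (T3".

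**Assumed, because the documents are silent:** two-sided alpha 0.05, baseline prevalence, event rates, and the strength of the baseline-to-termination association.

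**Step 1. Chance baseline gap.** SE of the difference in baseline proportions = √(2p(1−p)/n per arm).
- p = 0.5, n = 50: √(0.5/50) = 0.100. P(gap ≥ 10 points) = 2(1 − Φ(0.10/0.100)) = 32%.
- p = 0.5, n = 35: √(0.5/35) = 0.120. P = 40%.
- p = 0.3 or 0.7: SE 0.092 and 0.110, P = 28% and 36%.
- If only 25 per arm were analysed: 44% to 48% over the same prevalences.

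With equal prevalence at both time points, the expected carry-over is phi × gap, where phi is the correlation of the two binary values. A 10-point gap moves the unadjusted termination difference by 10 × 0.3 = 3 points at phi 0.3, or 10 × 0.5 = 5 points at phi 0.5.

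**Step 2. Precision.** Adjusting for baseline multiplies the variance of the risk difference by about 1 − phi², which is worth 100/(1 − phi²) youth in place of 100.

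| phi | variance factor | equivalent N |
|---|---|---|
| 0.2 | 0.96 | 104 |
| 0.3 | 0.91 | 110 |
| 0.4 | 0.84 | 119 |
| 0.5 | 0.75 | 133 |

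Simulation with no treatment effect and 50 per arm gave 0.97, 0.91 and 0.75 at phi 0.2, 0.3 and 0.5, in agreement.

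**Step 3. Power.** Scenario: 50% at baseline, 40% against 20% at termination. Within each arm, q1 and q0 (the termination risks with and without baseline suicidal thoughts) satisfy q1 + q0 = 2p and have the chosen odds ratio. Example, control arm, odds ratio 8: q1 ≈ 0.627, q0 ≈ 0.173, so phi = (0.627 − 0.173) × 0.5/√(0.4 × 0.6) ≈ 0.46. The closed-form power of the unadjusted test is 44.5% (35 per arm) and 59.0% (50 per arm). Simulation, 20,000 trials per cell, chi-square to baseline-stratified Mantel-Haenszel:

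| odds ratio (phi) | 70 analysed | 100 analysed |
|---|---|---|
| 3 (0.26) | 45% → 47% | 59% → 62% |
| 8 (0.46) | 46% → 51% | 60% → 67% |
| 15 (0.57) | 46% → 56% | 60% → 71% |

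Allowing for simulation error over repeated runs, the gain is about 2 points at 3, 5 to 9 points at 8, and 10 to 11 points at 15. A smaller run (2,000 trials) at an odds ratio of 2 gave 44% → 44% and 59% → 60%, essentially nothing. Type I error was 4.6% to 5.3% for both tests.

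**Step 4. A larger model.** Logistic regression on arm, baseline suicidal thoughts and five indicators for the four randomisation factors (assumed 40% prevalence, no prognostic effect, 30% event rate) gave likelihood-ratio type I error of about 6% to 8% for 50 to 100 youth, with one set of runs reaching 9.6% at 50.

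**The case against.** The strongest reply is that nothing here is invalid. Under randomisation the chi-square is unbiased on average and holds its error rate; chance imbalance is random error that the test already allows for. That stands. A reader might infer from the missing adjustment that the comparison is confounded or its p-value wrong. The documents do not support that: allocation is by chance, and in the simulations the mean adjusted and unadjusted risk differences agreed to within about 0.001. The point is one of efficiency and of how to read one realised dataset.

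Second, the gain may be negligible. It becomes material only at phi of about 0.4 or more, and nothing in the documents says where phi lies. A reader might take the figures at odds ratios of 8 or 15 as the expected loss; they are the favourable end of an assumed range. This also stands.

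Third, the time point and population are inferred. Termination is the natural reading, because the preceding sentence reports baseline and termination and a treatment comparison is informative only after baseline, but the sentence does not say so. If only youth in the clinical range are tested, 70 to 100 overstates the sample.

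Fourth, the outcome is not a listed endpoint, and the trial calls its own aim preliminary efficacy. That lowers the weight. It does not remove the point, because the baseline value costs nothing to use.

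**Conclusion.** The concern holds as a modest one. The SAP's between-arm test of suicidal thoughts ignores a baseline value that is collected, is not a randomisation stratum and is adjusted for nowhere else. The result is valid but less precise than it could be, and it retains any chance baseline gap. A gap of 10 points or more would occur in roughly 28% to 40% of trials of this size.

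The power gain from adjustment runs from about 2 points to about 11 points over odds ratios of 3 to 15. It rests on assumed event rates, 1:1 allocation, two-sided 5% alpha and 70 to 100 youth analysed. Type of self-harm, a stratification factor, may balance suicidal thoughts in part, which would reduce the chance gap; the documents give no way to quantify this.

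Two stronger conclusions should not be drawn. Being the only stated between-arm test on a suicide-related outcome does not make this a primary analysis: section 9 of the protocol names self-harm as primary. Nor does the case for adjustment extend to a logistic model carrying every randomisation factor, which did not hold the 5% level in the check at this sample size.

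**What to change.** - Compare suicidal thoughts at termination (T2) with a Mantel-Haenszel test stratified by baseline suicidal thoughts (yes/no), without continuity correction as in the figures above.
- Report the baseline-adjusted risk difference with its 95% CI. A risk difference shows the gain in precision directly. An odds ratio from a logistic model is conditional on baseline, and its standard error need not fall.
- Do not add all four randomisation factors to a logistic model at this sample size.
- State the time point, and whether the test uses all randomised youth or only those in the clinical range at baseline, with the number analysed in each arm.
- The SAP is written in the past tense, as already analysed. Keep the chi-square, show the adjusted result beside it, and label it as added later.

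The cost is two or three sentences in the SAP and one stratified table. No new data are needed, and the estimate can be computed from two 2×2 tables.

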# 3) Objectives\*

The study described in the protocol is a randomized trial at UM. The study will enroll 100 11-18 year old youth with a self-reported act of self-harm in the past 6 months and their families. This study is designed to refine and test the efficacy of a computer assisted culturally informed and flexible/adaptive intervention for Latino adolescents for whom self-harm behaviors are a health disparity—specifically, Latinas and sexual/gender minority youth. The specific aims of this study are:

- To build on the Computer Assisted CIFFTA intervention by creating a web-site and web-based delivery system and by adding content that is relevant for the factors that maintain self-harm in Latina adolescents (e.g., depression, family conflict, substance use, and emotion dysregulation) and for unique stressors often linked to sexual/gender minority youth and those exposed to trauma.
- 2) To investigate the preliminary efficacy of the Computer Assisted CIFFTA in reducing self-harm and in modifying the factors that place youth at risk for self-harm (e.g., depression, family conflict, substance use, and emotion dysregulation) when compared to controls (Treatment-As-Usual).
- 3) To investigate the linkages between co-existing problem areas (e.g., selfharm, risky sexual behavior, substance use) to see if there is evidence of a syndemic.
- 4) To investigate the relationship of culture-related variables (e.g., acculturation, familism, and Hispanic Stress) to the key factors hypothesized to contribute to self-harm behavior (i.e., depression, family conflict, substance use, and emotion dysregulation).

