### **Charge of the Board DSMB**

The purpose of the DSMB will be to provide oversight on the human subject issues described in the protocol, including review (overall and by condition) of the number and type of adverse and serious adverse events. The trial is focusing exclusively on two high risk groups, Hispanic females and Hispanic LGBT youth with a history of self-harm. Adverse events that will be monitored include, but are not limited to psychiatric hospitalizations, suicidal attempts, arrests and child abuse, including sexual abuse. The DSMB will be blinded to condition but will review the number of adverse and serious adverse events by condition in group format. If it becomes apparent that there may be an imbalance by condition, the DSMB will offer its recommendation to the PI regarding the conduct of the trial. Any action that results in the temporary or permanent suspension of the trial will be undertaken with consultation with the study's NIMHD project officer and University of Miami's IRB. The DSMB will provide a copy of the meeting's minutes to the PI.

The University of Miami IRB will provide general study oversight for all grant activities. The Principal Investigator will report DSMB activity to NIMHD as part of the Annual Progress Report.

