Lastly, to examine whether changes on the plausible mechanisms of action was associated with the likelihood of engaging in self-harm in the past month at termination in the full sample; after controlling for gender and LGBTQ status, a series of hierarchical logistic regressions were performed. With only two timepoints we could not conduct formal analyses of mediation, but we could explore whether the patterns of change were consistent with plausible mediators. In these models, self-harm in the past month was the binary outcome variable, LGBTQ status and gender were entered in Step 1 as covariates, and the proposed mechanism of action (i.e., depression, parent communication, family connectedness, and emotion regulation) were entered in Step 2.

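### The SAP's self-harm mechanism models have no small-sample safeguard: a real effect would be modestly overstated and the gender term may separate, and a Firth fit would remove most of this cheaply

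*SAP*

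**What the plan says.** The last paragraph of the SAP relates the proposed mechanisms to self-harm at termination: "a series of hierarchical logistic regressions were performed". The outcome is binary ("self-harm in the past month was the binary outcome variable"). For the predictors, "LGBTQ status and gender were entered in Step 1 as covariates", and then the mechanisms follow: "depression, parent communication, family connectedness, and emotion regulation) were entered in Step 2". The wording does not settle whether each mechanism has its own model or all four enter one model. The SAP names SPSS 29 and mentions no penalised, exact or bootstrap method and no rule for a covariate that separates the outcome. It treats these models as exploratory, because two timepoints do not allow a formal mediation analysis.

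On sample size, Protocol section 3 says "The study will enroll 100 11-18 year old youth". The number analysed at T2 is not given. The SAP expects some loss, since it models "whether baseline characteristics predicted those participants who successfully reached termination and T2 assessments". The only retention figure comes from an earlier trial, about "70% of the adolescent scheduled assessments 16 months after baseline" (Protocol section 10). On composition, the DSMB charge says "The trial is focusing exclusively on two high risk groups, Hispanic females and Hispanic LGBT youth". No event count, event rate or gender split appears in either document.

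**The concern.** Maximum-likelihood logistic regression is biased away from the null in small samples. The bias grows as events become fewer and predictors more numerous. If every member of a covariate group has the same outcome, the coefficient for that group has no finite estimate. With at most 100 youths, two binary covariates and one to four mechanism terms, both problems are possible here.

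Self-harm is the primary endpoint (Protocol section 9). Elsewhere the SAP gives it only descriptive rates by condition; the chi-square test by condition concerns thoughts of suicide. The mechanism models are therefore the SAP's only inferential analyses with self-harm as the outcome. Because they are exploratory, readers will rely mainly on the size of the odds ratios, and that is where the bias lies.

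**Working it through.** The documents give no odds ratio, event count or power figure for these models, so there is no planned figure to reproduce. The check is a simulation of maximum likelihood (ML) against Firth penalised likelihood.

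**From the documents.** N is at most 100; N = 70 applies the earlier trial's 70% to 100 youths. There are two Step 1 covariates and four mechanisms, giving 2 + 1 = 3 slopes if entered singly or 2 + 4 = 6 if entered together.

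**Assumed.** Event rate 10–40% (7–28 events at N = 70, 10–40 at N = 100). Male share 5, 10 or 20%, with all males LGBTQ, as the DSMB charge would imply. 35% of females LGBTQ. True odds ratio (OR) 1.0 for gender, 1.5 for LGBTQ status and 2.0 per SD for each mechanism. Correlation 0.4 between mechanisms. 800 data sets per scenario.

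**1. Bias in the mechanism OR, N = 70, 10% male.** Entries are exp(mean log OR). Brackets give the bias of the log OR, ln(estimate)/ln(2) − 1.

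| Event rate | ML, one mechanism | Firth, one | ML, four together | Firth, four |
|---|---|---|---|---|
| 10% | 2.22 (+15%) | 1.97 (−2%) | 3.01 (+59%) | 1.96 (−3%) |
| 20% | 2.17 (+12%) | 2.00 (0%) | 2.48 (+31%) | 1.97 (−2%) |
| 30% | 2.16 (+11%) | 2.02 (+1%) | 2.40 (+26%) | 1.99 (−1%) |
| 40% | 2.17 (+12%) | 2.03 (+2%) | 2.48 (+31%) | 2.10 (+7%) |

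Simulation error is small for single entry. At a 20% event rate the SD of the log OR is 0.40, so its standard error is 0.40/√796 = 0.014, or 2% of ln 2.

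At N = 100, across the male shares, ML gave 2.08–2.19 singly (+6% to +13% on the log scale) and 2.15–2.49 together (+10% to +32%).

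With a true OR of 1.0 (N = 70, 10% male), ML gave 0.98–1.00, so there is no inflation under the null.

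**2. Wider assumptions.** A separate simulation with n = 70–100, event rates 15–50% and 10–20% male gave an ML log-odds bias of about 4–22% singly and 6–33% with four together. Firth had the lower root mean square error (RMSE) in every scenario and near-zero bias in most. With a smaller true effect (log odds 0.5 per SD, n = 70 or 85, event rates 15–30%, 15% male), the single-mechanism bias was 9–14%.

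**3. RMSE, one mechanism, from the first simulation.** RMSE = √(SD² + bias²). At a 20% event rate, ML gives √(0.40² + 0.082²) = 0.408 and Firth gives √(0.35² + 0²) = 0.350, which is 14% lower. The same calculation at 10, 30 and 40% gives 15, 13 and 11% lower.

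**4. Separation.** In a group of g youths with event rate p, all share one outcome with probability (1−p)^g + p^g. For 7 boys (10% of 70):
- p = 0.1: 0.9⁷ + 0.1⁷ = 48%
- p = 0.2: 21%
- p = 0.3: 8%
- p = 0.4: 3%

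Simulated ML failures at N = 70 and 10% male with one mechanism were close to this, at 49, 19, 10 and 5%. With one or four mechanisms, 77–100% of those failures were separation of the gender term alone, and the mechanism coefficient stayed finite. Over all scenarios failures ran from 0% (N = 100, 40% events, 20% male) to 65% (N = 70, 10% events, 5% male). In the 15–50% event-rate simulation they ran from 0 to 30%.

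**5. What Firth does not repair.** At N = 70 and 10% male with one mechanism, the median ratio of upper to lower 95% limit for the gender OR was still about 45 to 270. In the sparsest case (10% events, 5% male) the gender OR was about 1.7 against a true 1.0.

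**The case against.** The strongest reply is that every quantity driving the size is assumed. Recent self-harm is an entry criterion (Protocol section 5), so the past-month rate at termination could be high. The 70% retention figure is from another trial at 16 months, whereas termination here is at 4 months. Sex and LGBT status are not eligibility criteria, so the male share is open, and an empty male non-LGBTQ cell does not by itself cause separation in a main-effects model. With 30–40% events and 20% male, failures fall to 0–1.4%. All of this stands, and it is why the point is conditional.

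The bias is also modest against sampling error. With one mechanism at 20% events it is ln(2.17/2.0) = 0.082 against an SD of 0.40, about one fifth. That stands too. It limits the importance of the point but does not make the planned fit the better one.

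The phrase about a series of regressions suggests one mechanism per model, which would avoid the larger bias. That is the more natural reading, but the text does not settle it.

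Three stronger readings are tempting. A reader might infer that the reported odds ratios are known to be inflated. The documents do not show this, because the inflation depends on a real effect and on unknown counts. A reader might infer that some fits must have failed. No event count or gender split supports that, and most simulated failures spared the mechanism estimate. A reader might also infer that penalisation fully cures sparse data. The wide gender intervals show otherwise.

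**Conclusion.** The concern holds in conditional form. The SAP fits logistic models to at most 100 youths without a small-sample safeguard. If a mechanism has a real effect, its log odds ratio is expected to be overstated by roughly 4–20% with one mechanism per model and by more with all four together. This takes 70–100 youths, event rates of 15–50% and 10–20% males; rates near 10% would be worse. There is no systematic push towards finding a mechanism where none exists.

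Under the same assumptions the gender term may separate in 0–30% of fits, usually leaving the mechanism estimate usable. Firth estimation performed better than the planned method throughout, even at N = 100 and 50% events, so the change is worth making. It is a low-priority improvement to an exploratory analysis and does not invalidate the models.

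**What to change.** Enter one mechanism per model and say so. Fit Steps 1 and 2 by Firth penalised-likelihood logistic regression, with penalised profile-likelihood 95% intervals and a penalised likelihood-ratio test for the Step 2 term. For each model report the number of youths, the number with past-month self-harm and the gender by LGBTQ cell sizes, so that readers can see how sparse the data are.

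The SAP is written in the past tense, so this means re-fitting existing data in an SPSS extension or another package, as well as changing the text. No new data are needed. The odds ratios will be slightly smaller, and intervals for sparse covariates will remain wide.
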